The recruitment strategy involves first identifying Veterans scheduled for a compensation examination for an MSD by reviewing chart and Compensation Clinic information about Veterans scheduled for these evaluations. A research assistant at the hub site will exclude people whose records preclude post-9/11 military service and mail recruitment letters. These potentially eligible Veterans will be mailed a letter from the mPIs explaining the basics of the study and that a member of the research team will call to further explain the study. A toll-free phone number will be included in the letter that Veterans can call to opt out of receiving the phone call or to express their interest in participating. Veterans who opt out will not receive any more study-related phone calls. A copy of the Study Information Sheet describing the study will be included with the recruitment letter.

At least four days after the recruitment letter is sent, research assistants will call Veterans up to three times to invite them to participate in the study. A four-day waiting period from the day the letter is mailed to the day of the call is sufficient to allow Veterans time to receive the letter in the mail, but not so long that Veterans are likely to have scheduled and completed their C&P exams before the recruitment call can be made. During this recruitment call, the research assistant will explain the study and further screen for eligibility. For eligible Veterans, the research assistant will conduct informed consent and baseline assessments during this phone call or subsequently. Although enrollment ideally occurs before the Compensation examination, Veterans will be allowed to enroll up to six weeks after recruitment letters are mailed. If a Veteran misplaces or has not received the Study Information Sheet, the Research Assistants will offer to mail another copy to the Veteran. The Veteran can choose to continue with the recruitment call or to wait until they receive the copy of the Information Sheet before continuing.

VA Staff:

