
Veterans

Inclusion criteria are:

- 1) Post-9/11 Veteran applying for MSD-related compensation, as ascertained from filed claim;
- 2) Reports a score of ≥ 4 (threshold for moderately severe pain) on the BPI's Pain Severity subscale (average of four pain intensity items);
- 3) Availability of a landline or cellular telephone for SBIRT-PM.

Exclusion criteria are:

- 1) Reports inability to participate during the study enrollment call;
- 2) Received three or more non-pharmacological pain treatment modalities (as previously categorized (111)) within the last 12 weeks from VA. Modalities include (1) primary care doctor visit for pain, (2) surgery for pain, (3) spinal cord stimulator, (4) injection for pain, (5) TENS, (6) Acupuncture/dry needling/Acupressure, (7) manipulation of spine or joints, (8) massage therapy, (9) yoga, (10) tai chi or Qigong, (11) Reiki, (12) Biofeedback, (13) education about how to cope with pain, (14) counseling for pain, (15) relaxation techniques for pain (such as guided imagery), (16) mindfulness or meditation, (17) hypnosis or hypnotherapy (18), exercises like strength training or stretches to help with pain.
- 3) Participation in another PMC3 study as evidenced by a research protocol alert for that study at the time the study invitation letter is mailed.

VA Clinicians and Administrators (UG3)

VA clinicians and administrators in Compensation and Pension and Primary Care will complete semi-structured key informant interviews and brief surveys to assess the organization and coordination of pain management services at each of the study sites.

These participants are invited by the investigators because they are employees at the study sites and have some clinical or administrative involvement with Veterans who have MSD.

SBIRT-PM Intervention.

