We also will collect other data about SBIRT-PM implementation. Specifically, we will report the percentage of participants who received different "doses" of the intervention (i.,e., 0, 1, 2, 3, or 4 sessions). We also will track the percentage of each counselor's assigned Veterans who receive counseling and the percentage whose first counseling session is followed by a second. In our pilot, 80% of participants received the assigned counseling, and 55% of those who received any counseling had at least two sessions. If a counselor falls below 70% of participants receiving any counseling within 12 weeks or below 50% of a second session among those with a first, we will take the following steps: 1) compare that counselor's procedures to "best practices" by other counselors. Such best practices might include time of day Veterans are called, and the negotiation around scheduling the calls; and 2) contact the site PI to determine if sub-optimal engagement is a site-specific issue. Two examples of site-specific issues are cell phone reception and local VA hospital reputations. In very rural areas, poor cell phone coverage makes participation more difficult, and it may be more difficult to engage Veterans when the VA facilities in their local communities have a damaged reputation.

Finally, using the ITRS, we will independently rate a random sample of about 10% of the SBIRT-PM sessions (n = 220) for the counselors' adherence and competence in delivering the intervention to demonstrate the sessions were delivered as intended.

Study Evaluations

Assessments

Assessment Name/Domain	Data Source	Baseline	12-wk	Time to complete (mins)
Socio-demographic Characteristics	Self-Report	x		2
Psychiatric and Substance Use Diagnoses	VA EHR -structured data (e.g. clinic codes)	x		
Characteristics of Musculoskeletal Disorders	VA EHR, Service-connection exam	x		
Distance to nearest VA Facility	VA EHR		x	
Brief Pain Inventory	Self-report	x	x	5
PEG	Self-report	X	X	1
High Impact Pain questionnaire	Self-report	X	X	1
Opioid Medications Dispensed in Morphine Equivalent Daily Dose	VA EHR	x	x	
Non-opioid Medications Dispensed	VA EHR	x	x	
Pain Management Service Use—VA services	VA EHR -structured data (e.g. clinic codes)	x	x	
Pain Management Service Use---VA and non-VA services	VA EHR with Natural Language Processing	x	x	
Self-reported VA and non-VA service use	Self-report	x	x	3
ASSIST	Self-report	x	x	10
Prescribed Opioids or Stimulants	Self-report	x	x	2

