Nail clippings for drug/etoh use metabolites	Biological	x	x	
Substance Use/Mental Health Treatment Service Utilization – VA services	VA EHR -workload data and clinic codes	x	x	
Self-reported VA and non-VA substance use service use	Self-report	x	x	3
AUDIT-C	Self-report	X	X	2
Prescribed Opioids or Stimulants	Self-report	x	x	1
PHQ-9 (depression)	Self-report	x	x	5
EQ-5D-5L	Self-report	x	x	5
Work Productivity and Activity Impairment Questionnaire	Self-report	x	x	2
Motivation for engaging in pain treatment	Self-report	X	X	1
COVID-19 questionnaire	Self-report	X	X	5
Total BL interview time = 48 minutes				

UG3 Preparation Assessments and End-of-Study Assessments

Measures Described Earlier in UG3 Stage of RCT preparation			
		UG3 preparation phase	End of UH3 Study
Qualitative Interviews of Stakeholders	Self-report	x	x
Post-intervention Interview of SBIRT-PM-treated Veterans	Self-report	x	
Relational Coordination Survey of Key Stakeholders	Self-report	x	x
Treatment Fidelity Measure: Independent Tape Rater Scale	audio recorded SBIRT-PM session ratings		x

Measures to Characterize the Sample.

- Socio-demographic Characteristics. A research assistant will collect socio-demographics (age, gender, race, ethnicity, marital status, education, employment status, legal status, and military history) from Veterans during baseline assessment.
- Medical Diagnoses. We will extract medical diagnoses from electronic health records and the VA Corporate Data Warehouse. We will identify psychiatric (e.g., depression, anxiety, Traumatic Brain Injuries,(120, 121) and PTSD(122, 123)) and substance use disorders in the EHR and VA Corporate Data Warehouse by their ICD-9 and 10 codes. We decided against more direct measures of psychiatric conditions (e.g. the PTSD Checklist) to minimize participant burden and reactivity. In order to increase the sensitivity of our detection of psychiatric conditions, we will extract the service-connection claims data from the Veterans Benefits Management System for study participants at the end of their study participation. New recipients of service-connection receive it for an average of 5.25 distinct claims,(40) and many Veterans file both MSD and claims for mental conditions at the same time. This will identify Veterans with psychiatric disorders who were diagnosed during their service-connection examinations but do not have a diagnosis in VA treatment records because they were not treated for their mental health condition.

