- Characteristics of Musculoskeletal Disorders. We will determine the diagnostic group of MSD assigned to participants in the EHR by using ICD-9 or 10 codes. Major groups are back pain, neck pain, and osteoarthritis. Other categories will be combined as suggested by their frequency and co-occurrence with other MSD. These include non-traumatic joint disorders, osteoporosis, sprain and strain, traumatic joint disorder, spinal cord injury, fibromyalgia, rheumatoid arthritis, temporal mandibular disorder, lupus, gout, and MSD multimorbidity (more than one MSD diagnosed). The broad MSD groups will be considered as potential moderators of treatment effect in the analyses. In addition, compensation examiners complete a detailed, structured form, the Disability Benefits Questionnaire (DBQ), for each Veteran they evaluate. From these forms, we will extract structured notations of the examination findings. Finally, we will obtain the percentage service-connection awarded from the Veterans Benefits Administration System (VBMS) as it changes over the course of study participation (e.g. before and after the determination) and all delineate service-connected conditions.
- Distance to nearest VA Facility. We will calculate the distance from the Veterans' address, as indicated in the EHR, to the nearest VA facility using procedures developed by the Planning System Support Group.

Pain Measures:

- Brief Pain Inventory (BPI). The Brief Pain Inventory(124) (BPI) is a validated instrument to assess chronic non-cancer pain that yields two subscales. One measures pain severity (4 items on a 0-10 scale) and the other assesses pain interference with life activities (7 items on a 0-10 scale), both using a 24-hour recall period. BPI Pain Severity subscale will serve as our primary pain outcome for the trial; pain interference subscale will serve as a secondary outcome. The BPI is a reliable measure and responsive to change.(125) The BPI is endorsed by the Initiative on Methods, Measurement, and Pain Assessment in Clinical Trials (IMMPACT) group(126) as a preferred measure of pain-related functioning IMMPACT recommendations have specified a score change that would represent a minimally clinically important difference (i.e., 30% reduction in pain severity and 1-point reduction in pain interference), which will be used in our cost analyses.(127)

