To examine feasibility of enrollment, counseling participation, and pilot study retention, descriptive data (frequency counts, percentages, means, and standard deviations) were calculated. Descriptive data were also provided for study outcomes. Changes in BPI scores and the number of nonpharmacological pain treatments utilized from baseline to week 12 were calculated and examined using the Wilcoxon signed rank sum test, the nonparametric equivalent of the paired *t*-test. The percentages of participants with problematic substance use were compared between baseline and week 12 using χ^2 tests. The *p* values should be interpreted with caution given lack of a control group and limited statistical power. For qualitative analysis, transcribed interviews were analyzed using standard qualitative analysis methods by which 2 coders independently reviewed the transcripts, creating code definitions as concepts emerged inductively from the data. Codes were refined until a final coding structure was reached, capturing the major concepts in the data, which was then applied to all transcripts.

Analysis of Qualitative Data.

We hypothesize that implementation of SBIRT-PM will be associated with changes in the way staff interact with each other, how they think about pain treatment, and how they connect service-connection claimants to treatment. To test these hypotheses, we will compare results from the Relational Coordination Survey administered before the RCT with survey results from the same participants afterwards using paired-samples *t*-tests. The comparison of semi-structured interviews with stakeholders and staff before and after the RCT will involve describing differences in themes identified at the two timepoints.

Analyses of NLP Algorithms

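### Does selecting on BPI severity at entry call for a regression-to-the-mean warning beside the single-arm test of BPI change?

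*Combined protocol and SAP*

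**What the plan says.** - Inclusion and Exclusion Criteria (UG3): entry requires a BPI Pain Severity score of at least 4, described as the "threshold for moderately severe pain".
- Pain Measures: "BPI Pain Severity subscale will serve as our primary pain outcome for the trial". The recall period is 24 hours. The same paragraph takes a "30% reduction in pain severity" as the minimally important difference.
- Specific Aims: every enrolled Veteran is offered the intervention and is assessed at baseline and week 12, so the pilot has one arm. The trial being prepared compares the intervention with usual care.
- Screening and Recruitment: eligibility is screened on the recruitment call, and for eligible Veterans "the research assistant will conduct informed consent and baseline assessments during this phone call or subsequently". Whether the qualifying BPI score is carried forward as the baseline is not stated.
- Data Analysis: "Changes in BPI scores and the number of nonpharmacological pain treatments utilized from baseline to week 12 were calculated and examined" with the Wilcoxon signed rank test. The section then cautions that the p "values should be interpreted with caution given lack of a control group and limited statistical power".

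**The concern.** Choosing people because a noisy score is high, and then comparing that same score with a later one, produces an expected fall even when nothing has changed. Here the selecting measure and the tested measure are the same subscale, a 24-hour recall leaves room for day-to-day noise, and there is no comparison arm to absorb the artefact.

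The caveat does not mention selection on the outcome. Of its two reasons, limited power warns of missed effects, whereas selection at entry would create an apparent benefit. Because BPI severity is the main pain outcome for the trial, a reader could take a significant fall in the pilot as a sign of efficacy when some of it comes from the entry rule.

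**Working it through.** **Was the qualifying score the baseline?** The recruitment text allows baseline on the screening call or later. The Assessments table lists the "Brief Pain Inventory" once at baseline (5 minutes) and has no screening column. Its timed rows add to 2+5+1+1+3+10+2+3+2+1+5+5+2+1+5 = 48, matching "Total BL interview time = 48 minutes" with the BPI counted once. That fits re-use of the screening score, and it fits a separate untimed screening BPI equally well. The document does not settle the question.

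**How large could the artefact be?** The document gives no power, effect-size or variance figure for this test, so there is nothing to reproduce. Every input below except the cut of 4 is assumed: unselected mean μ 4 to 6, SD 1.5 to 2, correlation r between the qualifying and week-12 scores 0.6 to 0.9, no true change, normal scores.

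With c = (4 − μ)/SD and λ = φ(c)/(1 − Φ(c)):

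- expected fall = SD × (1 − r) × λ
- baseline mean = μ + SD × λ

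Central case, μ = 5, SD = 2, r = 0.7: c = −0.5, λ = 0.3521/0.6915 = 0.509. Fall = 2 × 0.3 × 0.509 = 0.31. Baseline mean = 5 + 2 × 0.509 = 6.02. The fall is 5.1% of baseline.

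The last two columns give the simulated share of null pilots with a significant fall (Wilcoxon, two-sided 5% assumed, 1,500 runs per cell; nominal 2.5% in that direction). Two sample sizes are shown because Specific Aims gives 5 × 8 = 40 and the counselor-training and piloting section allows 10 × 8 = 80.

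| μ | SD | r | Fall | Baseline mean | Fall, % of baseline | n = 40 | n = 80 |
|---|---|---|---|---|---|---|---|
| 4 | 2.0 | 0.6 | 0.64 | 5.60 | 11.4% | 60% | 92% |
| 4 | 1.5 | 0.6 | 0.48 | 5.20 | 9.2% | 62% | 91% |
| 5 | 2.0 | 0.7 | 0.31 | 6.02 | 5.1% | 24% | 40% |
| 6 | 2.0 | 0.7 | 0.17 | 6.58 | 2.6% | 11% | 16% |
| 6 | 1.5 | 0.9 | 0.03 | 6.27 | 0.4% | 5% | 5% |

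Over the whole grid the fall is 0.03 to 0.64 points, and the share significant is 4% to 62% at n = 40 and 5% to 92% at n = 80. The top rows need μ = 4, which means half of those screened fail the pain criterion. The document gives no screen-failure rate.

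**Against the stated benchmark.** A 30% reduction from 5.60 is 0.30 × 5.60 = 1.68 points. The largest artefact, 0.64, is 0.64/1.68 = 38% of that. In the central case it is 0.31/(0.30 × 6.02) = 0.31/1.81 = 17%.

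**If the baseline was asked again.** With independent errors the expected fall is zero (simulated 0.001, against 0.305 with re-use, in the central case). If the errors of the two askings correlate at k, as they might within one call, the fall is k times the re-use value. With k = 0.8 (assumed) that is 0.8 × 0.31 = 0.24 in the central case and 0.8 × 0.64 = 0.51 at the top. A second asking removes the artefact only when its errors are independent of the first.

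**What depends on the test?** The UG3 milestone table lists approvals, procedures, site visits, interviews, cost methods, hiring, training and piloting, and the language-processing algorithm. None is met or missed according to BPI change. The Data Analysis section opens with feasibility of enrollment, counseling participation and retention.

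**The case for a change.** The best argument for a change is that the existing caution is generic and attached to p values only, while regression to the mean moves the mean change itself, which is reported descriptively as well. The direction is known, it favors the intervention, and at 80 participants with the less favorable assumptions a significant fall would be the usual result under no effect. Naming the mechanism would take one sentence.

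Much of this stands. The caveat is less specific than it could be, and a significant pilot p value for BPI severity is weak evidence. But the reason given for caution, no control group, applies to the mean change as much as to its p value, and it warns of exactly this kind of spurious improvement. To contrast selection bias with limited power alone is to skip that half of the sentence. Regression to the mean is one of several things an absent control group leaves open, alongside natural course and other treatment, and the plan need not list each.

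The status of BPI severity as the main pain outcome belongs to the planned comparison with usual care. There both arms enter by the same rule, so the artefact is shared and cancels from the comparison. Whether the pilot score was re-used is a fact the investigators hold. It is properly stated when the results are described, and a conditional warning in the plan would be a poor substitute for it.

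**Conclusion.** The observation is accurate but leads to no change. Entry does select on the tested subscale, the pilot has one arm, and the document is silent on whether the qualifying score was the baseline. If it was, or if it was asked again with correlated errors, some fall in BPI severity is expected without any effect: 0.03 to 0.64 points with re-use under the assumed ranges, a size the document itself cannot supply. That is enough to produce a small p value in some scenarios, but well short of the 30% reduction cited. BPI interference is touched only through its correlation with severity.

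The plan already tells readers to discount these p values because there is no control group, the analysis is descriptive in purpose, and no milestone turns on it. What remains is a reporting detail that an analyst fills in by saying when the baseline BPI was taken. The conclusion rests on the pilot being read as the feasibility study it is described as. If its BPI change were offered as evidence of efficacy, the point would matter more.

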- Self-Reported Use of Pain Treatment Services(129): The PMC3’s phenotype and outcomes workgroup developed the “Use of nonpharmacological and self-care approaches” questionnaire to collect information about patients’ use of 13 different pain treatments. The instrument was modified for this study to collect information over the past 3 months (instead of past year), and to include several additional categories. In order to assess costs of services as a result of counseling, we included questions asking, for each treatment received, if it was in an individual or group setting and if the treatment was done at home (self-care). We will also ask if the treatment was received at the VA or an “other” provider and the number of times in the past three months it was received. Categories include evidence-based and complementary and integrative modalities for pain available at VA sites and in the community, and include (1) over-the counter medications (2) opioid medications for pain (3) other prescribed medications for pain (4) ER/urgent care visits for pain (5) primary care doctor visit for pain (6) surgery for pain (7) spinal cord stimulator (8) injection for pain (9) TENS (10) Acupuncture (11) dry needling (12) Acupressure (13) manipulation of spine or joints (14) massage therapy (15) yoga (16) tai chi or Qigong (17) Reiki (18) Biofeedback (19) education about how to cope with pain (20) counseling for pain (21) relaxation techniques for pain (progressive relaxation, guided imagery, visualization, deep breathing) (22) mindfulness or meditation (23) hypnosis or hypnotherapy (24) walking to help with pain (25) exercises like aerobics, strength training or stretches to help with pain, (26) other treatments for pain

Substance Use Measures:

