We will identify the use of non-pharmacological pain modalities through self-report from the participants as well as two different approaches to the extraction of healthcare utilization data from electronic medical records. Medical record extraction of 1) Structured data - stop codes indicating use of these modalities, and 2) Unstructured data - domains identified in the application of the NLP method to the medical record data of study participants. Two independent researchers will identify words/snippets that suggest use of specific non-pharma modalities and rate enough snippets to have software reliably generate an algorithm to rate all patients included in the study on each modality (machine learning). As we expect false positive reports of use of a modality to be unlikely, identification of use during an assessment period by any of the three methods (self-report, medical record stop codes and NLP) will be considered use. The agreement between these different measures will be described by crosstabs.

References

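### The plan states no rule that leaves SBIRT-PM sessions out of the pain-treatment count, so study calls could raise the week-12 count but not the baseline count

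*Combined protocol and SAP*

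**What the plan says.** **Counting rule (Analyses of NLP Algorithms).** Use of a modality is sought in self-report, stop codes and NLP of the record. The rule is that "identification of use during an assessment period by any of the three methods (self-report, medical record stop codes and NLP) will be considered use", and the reason given is "As we expect false positive reports of use of a modality to be unlikely". Agreement between sources is to be described by crosstabs.

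**Test (Data Analysis).** For the treatment count, the plan reports that changes in "the number of nonpharmacological pain treatments utilized from baseline to week 12 were calculated and examined using the Wilcoxon signed rank sum test"; BPI is handled the same way. No source is named for this count. The section asks for caution with p values because there is no control group and power is limited.

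**Self-report (Self-Reported Use of Pain Treatment Services).** "The instrument was modified for this study to collect information over the past 3 months". The categories include "19) education about how to cope with pain (20) counseling for pain". For each treatment the questionnaire asks about setting, VA or other provider, and number of times.

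**Eligibility (Inclusion and Exclusion Criteria).** The exclusion for Veterans who "Received three or more non-pharmacological pain treatment modalities" lists "13) education about how to cope with pain, (14) counseling for pain" among those modalities.

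**Intervention.** Contact with the counselor follows baseline (Specific Aims) and runs for 12 weeks (Enrollment). In the Initial Session the counselor explains how pain can be managed and what the non-drug treatments do. Follow-up Sessions describes the later calls as counseling by phone. Under Coordination with PACT Providers, each session produces a counselor note in the electronic record.

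**The concern.** SBIRT-PM is meant to lead Veterans to pain services, and the number of those services is a tested outcome. Read literally, the counting rule allows the intervention to be one of the services. A Veteran asked at week 12 about pain counseling in the past three months could correctly say yes on the strength of the study calls alone.

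The timing turns this into bias. Over-reporting that was equal at both visits would cancel in the change. Study calls cannot fall in the baseline recall window, while the week-12 window covers nearly all of them. With one arm, nothing else in the design would reveal or remove the shift. The crosstabs would show that sources disagree but would not correct the count, and the caution on p values does not concern this mechanism.

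**Working it through.** **1. Is an exclusion stated?** The sections that define or use the count were compared.

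| Source | What the plan provides | Does it keep SBIRT-PM out? |
|---|---|---|
| Self-report | VA or other provider, setting, number of times | No. The calls come from a VA hub, so a VA answer does not isolate them |
| Stop codes | Workload data and clinic type | Not stated. The code for SBIRT-PM encounters is not given, so this route is possible but unproven |
| NLP | Tuning for positive predictive value, a current-use target, removal of routine history-taking, training snippets from primary care notes, note type as a classifier feature | Partly. Note type is a feature, not an exclusion |

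No section leaves out study sessions. Self-report is the clearest route, and the pain-counseling item is more plausible than the coping-education item.

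**2. Size of the shift.** The plan gives no expected change or power for this count, so there is no figure to reproduce. Per item:

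spurious mean change = c × q × (1 − b)

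- c = share counseled. SBIRT-PM Clinician Supervision reports 80% in *our pilot*; using it here is an assumption.
- q = share of the counseled whose calls are counted. Unknown.
- b = share already counted on that item for another reason. Unknown.

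With q = 1 and b = 0, the change is 1.00 × 1 × 1 = +1.00 if all are counseled, and 0.80 × 1 × 1 = +0.80 if 80% are.

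**3. Illustration, no true change.**
- n = 5 × 8 = 40 (Specific Aims), no dropout, c = 0.80, one item affected.
- 18 modalities, taken from the eligibility list because the plan does not say which self-report categories enter the count.
- Assumed: personal rates of use follow a gamma distribution; use is drawn independently at each visit; two-sided Wilcoxon signed-rank test at 0.05, zeros dropped, tie-corrected.
- b = baseline mean / 18.

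The shift is 0.80 × q × (1 − b). For example, a mean of 1.2 gives b = 1.2/18 = 0.067, and at q = 100% the shift is 0.80 × 0.933 = +0.75.

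| Assumed baseline mean | b | Shift at q = 25%, 50%, 100% | Rejection at q = 25%, 50%, 100% |
|---|---|---|---|
| 1.2 | 0.067 | +0.19, +0.37, +0.75 | about 12%, 35%, 88% |
| 3 | 0.167 | +0.17, +0.33, +0.67 | about 8%, 15–19%, 51% |
| 5 | 0.278 | +0.14, +0.29, +0.58 | about 7%, 12%, 34% |

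Without contamination, rejection is about 5%. Changing the gamma shape moves the cells by up to about 7 points (50–57% at mean 3, q = 100%).

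**4. A second model.** Poisson counts with mean 2 or 4 and within-person correlation 0.5, otherwise the same n and c, gave 10–13%, 22–37% and 67–92% at q = 25%, 50% and 100%. The direction agrees, and the assumed distribution again drives the rate.

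**The case against.** Several points on the other side stand.

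- **The rule may exist elsewhere.** The questionnaire script, the annotation guidelines and the standard operating procedures are not reproduced. The finding is that these documents state no rule, not that none was applied.
- **The intent points to an exclusion.** The questionnaire was extended "In order to assess costs of services as a result of counseling", which treats counseling as the cause of service use. That supports the fix but is not a counting rule.
- **The link to the test is not written.** The test is reported in the past tense without a source. The any-of-three rule is in the future tense under a separate heading. If the tested count came from structured records alone, the self-report route would not reach it.
- **Veterans may not report the calls.** The sessions are motivational interviewing about engagement and access. Whether Veterans would call that pain counseling is unknown.
- **The stakes are limited.** This is a feasibility pilot with a warning on p values, and no planning-phase milestone depends on this test.

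A reader might infer that study sessions were in fact counted, that all three sources are contaminated, or that a significant rise in the count is an artifact. The documents support none of these. They show an opening through self-report, a partly guarded route through NLP and an unproven one through stop codes. They give no value for q.

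**Conclusion.** The gap holds as a missing rule. As written, the plan allows truthful reports of study calls to raise the week-12 count and not the baseline count. Whether this reached the Wilcoxon test depends on the unnamed source of the tested count.

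The size is unknown. The +0.80 figure should not be read as an upper bound, because it rests on a counseling rate that may not be this study's. The bound is +1.00 per item if all are counseled. Across assumed baseline means of 5 down to 1.2, the illustrative rejection rates are about 7–12%, 12–35% and 34–88% at q = 25%, 50% and 100%. They show that the effect could matter, not that it did. They also ignore the eligibility limit on VA modalities, which could itself make counts rise after baseline through selection.

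Severity is minor to moderate: an exploratory test, not tied to a milestone, with an inexpensive remedy.

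**What to change.** (a) In Analyses of NLP Algorithms, state that SBIRT-PM sessions and encounters are not themselves use of a pain modality in self-report, stop codes or NLP. Genuine use of another service that is documented in a counselor note may still count; barring those notes altogether would remove real uptake at week 12 only.

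(b) In Data Analysis, name the source of the count used in the Wilcoxon test.

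(c) If self-report was collected without that instruction, repeat the baseline to week-12 test on a count that omits the pain-counseling and coping-education items at both visits. A table of these two items by number of sessions received may be added as description only: more sessions should also bring more real uptake, so it cannot separate the two.

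The cost is two sentences, an encounter filter and one rerun, with no new data. The downside of (c) is that it also drops genuine pain counseling or education received outside the study.
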